9.5.2.2. Time to first postsurgical opioid consumption comparing EXPAREL to 0.25% bupivacaine HCl

Time to first opioid consumption will be calculated in hours as the date and time of the first opioid medication taken post-surgery minus the date and time of end of surgery. If a subject does not have an opioid usage post-surgery, the time to first opioid consumption will be censored at the date of End of Study. For this derivation, the opioid consumption recorded on both Breakthrough Pain Medications and Prior/Concomitant Medications CRF pages will be considered.

Time to first opioid usage will be analyzed by the Kaplan-Meier survival analysis. Median time and the log-rank test comparing EXPAREL and 0.25% bupivacaine HCl will be presented. The log-rank test will be stratified by the age and height group (Section 9.5.3). Cox proportional hazards regression with treatment (EXPAREL, EXPAREL admixed with 0.25% bupivacaine, and 0.25% bupivacaine HCl) as factors and categorical investigator site, continuous age and height as covariates will also be performed. The number (and %) of subjects with opioid pain medication post discharge as well as the number (and %) of subjects without opioid pain medication post discharge will be presented for each treatment group.

9.5.2.3. AUC of the NRS pain intensity scores from 0 to 96 hours post-surgery comparing EXPAREL to EXPAREL admixed with 0.25% bupivacaine HCl

To examine differences between EXPAREL and EXPAREL admixed with 0.25% bupivacaine HCl, the same ANCOVA model as for the primary efficacy endpoint will be used. The LS mean difference between EXPAREL and EXPAREL admixed with 0.25% bupivacaine HCl groups, and two-sided 95% CI for the LS mean difference will be presented.

In addition to the presentation of the difference, the percent reduction in AUC will also be presented. The % reduction is derived as follows,

% Reduction = $\{LS Means_{EXP+Bup} - LS Means_{EXPAREL}\}/LS Means_{EXP+Bup}$.

9.5.2.4. Duration of the motor block comparing EXPAREL to EXPAREL admixed with 0.25% bupivacaine HCl (Cohort 1 only)

Duration of motor block will be analyzed by the Kaplan-Meier survival analysis. Although duration can be captured as left, right, or interval censored (Section 6.3.1), all these censored durations will be considered right censored for the programming purpose, because all these censoring implies that the actual duration is longer than the observed censored duration. Median time and the stratified log-rank test comparing EXPAREL and EXPAREL admixed with 0.25% bupivacaine HCl will be presented.

In addition to the presentation of the median, the ratio of EXPAREL to 0.25% bupivacaine HCl in motor duration median will be presented. The ratio is derived as follows,

 $Ratio = (Median_{EXPAREL}/Median_{EXP+Bup})$

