6.3. Pharmacodynamic Assessments (Cohort 1 only)

Time of onset/offset is collected on the corresponding "PD Assessment – Onset/Offset Sensory/Motor Block" eCRF.

6.3.1. Assessment of Sensory Block:

Sensory function for the sciatic and saphenous nerve will be assessed independently using a wooden tongue depressor and ice. This assessment will evaluate light touch and cold sensation.

Sensory function assessment will include the following four locations:

- 1. Saphenous proximal Medial aspect of the lower leg (3-4 cm below the knee)
- 2. Saphenous distal Medial aspect of the lower leg (3-4 cm above ankle)
- 3. Sciatic proximal Lateral aspect of the lower leg (3-4 cm above ankle)
- 4. Sciatic distal Sole of the foot

The tongue depressor application and ice will be performed at predose, 15 min, 30 min, 45 min, 1 h, 2 h, 8 h, 12 h, 24 h, 30 h, 48 h, 60 h, 72 h, 84 h, 96 h, 120 h, 144 h, and 168 h hours from the end of the nerve block procedure, or until full sensory function has returned to baseline (preblock) levels in two consecutive evaluations. Additional unscheduled assessments may be performed, particularly around the surgery if no onset of block is noted on the last scheduled assessment prior to surgery.

Onset of sensory block (sciatic and saphenous nerve tracked independently) will be defined as the earliest timepoint with loss of EITHER light touch sensation OR cold sensation in EITHER proximal OR distal locations at any time. If onset time is not achieved, it will be considered censored at the last onset assessment time prior to surgery. **Offset of sensory block** (sciatic and saphenous nerve tracked independently) will be defined as recovery of BOTH light touch

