sensation AND cold sensation in BOTH proximal and distal locations on two consecutive recovery assessments (excluding Not Done assessment). After offset of all sensory assessments are noted (on 2 consecutive assessments for all 4 locations), no subsequent assessments will be conducted. If offset time is not achieved, it will be considered censored at the last offset assessment time after surgery. If the patient's sensory block is recovered at the last assessment to confirm, the sensory block is considered recovered at this last time point. **Duration of sensory block** will be defined as the time between onset and offset of the sensory blocks for each nerve individually. If onset is not achieved, duration will be calculated from the surgery start time through the offset time, left censored. If both onset and offset assessment time, interval censored. See Section 9.5.2.4 for how the censoring is handled in the analysis. If postdose onset assessments are completely missing, time to onset will be set to missing.

6.3.2. Assessment of Motor Block:

Motor function (onset and offset of motor block) will be assessed using the 2-point scale on the side of the block. This will be used to determine the onset and duration of motor blockade.

Motor function will be assessed using a 2-point scale. The motor function test will be performed at predose, 15 min, 30 min, 45 min, 1 h, 2 h, 8 h, 12 h, 24 h, 30 h, 48 h, 60 h, 72 h, 84 h, 96 h, 120 h, 144 h, and 168 h from end of block procedure, or until full motor function has returned to pre-dose levels in two consecutive evaluations. Additional unscheduled assessments may be performed, particularly around the surgery if no onset of block is noted on the last scheduled assessment prior to surgery.

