Onset of motor block will be defined as the earliest timepoint with 2-point score of 1- Partial or no foot movement as opposed to 0- Complete foot movement. If subject does not experience loss of motor, their onset will be censored at their last available motor assessment time point prior to surgery. **Offset of motor block** will be defined as resolution of motor block at foot, first time point of the two consecutive recovery assessments (score 0- complete foot movement) (excluding Not Done assessment). If offset time is not achieved, it will be considered censored at the last offset assessment time after surgery. After offset of motor block is noted (on 2 consecutive assessments), no subsequent assessments will be required. If the patient's motor block is recovered at the last assessment to confirm, the motor block is considered recovered at this last time point. **Duration of motor block** will be defined as time between onset and offset of motor block. The censoring and missing data rule for the duration of sensory block also applies to the duration of motor block.

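### SAP 9.5.2.4 right-censors block durations whose offset was recorded, on a rationale that fails when onset was not achieved, and the SAP does not say which subjects this covers

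*SAP*

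**What the plan says.** SAP 6.3.1 sets the rule for sensory block: "If onset is not achieved, duration will be calculated from the surgery start time through the offset time, left censored". SAP 6.3.2 extends it: "The censoring and missing data rule for the duration of sensory block also applies to the duration of motor block". SAP 9.5.2.4 then recodes left-, right- and interval-censored durations alike: "all these censored durations will be considered right censored for the programming purpose, because all these censoring implies that the actual duration is longer". SAP 9.7.1 refers to 9.5.2.4 for censoring of sensory durations too.

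The definitions that decide who is affected are these:

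- Motor onset (6.3.2): "Onset of motor block will be defined as the earliest timepoint with 2-point score of 1- Partial or no foot movement". No pre-surgery limit is given.
- Sensory onset (6.3.1): "loss of EITHER light touch sensation OR cold sensation in EITHER proximal OR distal locations at any time".
- Motor onset not seen (6.3.2): "If subject does not experience loss of motor, their onset will be censored at their last available motor assessment time point prior to surgery". Section 6.3.1 has a matching pre-surgery cut-off for sensory block.
- Motor offset (6.3.2): "resolution of motor block at foot, first time point of the two consecutive recovery assessments".

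The block is given 90 ± 30 min before surgery (SAP Table 1 footnotes), and no block tests are done during surgery (Protocol Table 2, footnote c). Motor-block duration is the fourth secondary endpoint, the last step of the testing hierarchy in SAP 9.5, and is measured in Cohort 1 only, with about 20 subjects per arm.

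**The concern.** Right censoring says that the duration exceeds the entered value by an unknown amount. That is correct when follow-up ends with the block still present. When onset was not achieved but recovery was recorded, the end of the block is known and only its start is uncertain. The duration is then bounded above, and the entered value may be too long. SAP 6.3.1 itself labels this case left censored, which fits poorly with a rationale that the truth is always longer.

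The definitions also allow two codings of the same data.

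- **Reading A:** onset must be seen before surgery. A block first recorded afterwards counts as onset not achieved, and its recorded recovery becomes a non-event.
- **Reading B:** the rule reaches only subjects never seen blocked. They may then enter with a positive censored duration for a block that was never observed.

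The reported estimates are the Kaplan-Meier medians and their ratio, and with about 20 per arm a few recoded subjects can move a median.

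**Working it through.** The documents give no power, event count or median for block duration, so there is no planned figure to reproduce.

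**1. Bounds on the duration.** Measure time in hours from end of block. Let L be the last negative look, P the first positive look, I the incision and R the recorded offset. Onset lies in (L, P], so duration, taken to the recorded offset as the SAP does, lies between R − P and R − L. The rule enters R − I and treats it as open-ended.

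| Onset | True duration against R − I |
|---|---|
| Before incision | Longer, by at most I − L |
| After incision | Shorter, by up to P − I |
| Never | No block duration; entered value too long |

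**2. Worked example.** No block is seen through 1 h, incision is at 1.5 h, the foot is blocked at 8, 12 and 24 h, and recovery is seen at 30 and 48 h. So L = 1, I = 1.5, P = 8, R = 30.

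- True duration: 30 − 8 = 22 h to 30 − 1 = 29 h.
- Reading A enters 30 − 1.5 = 28.5 h, right censored. It is at most 29 − 28.5 = 0.5 h short and up to 28.5 − 22 = 6.5 h too long.
- Reading B enters 30 − 8 = 22 h as an event.
- If a recovery-room look at 3 h is the first positive, the minimum is 30 − 3 = 27 h and the excess is at most 28.5 − 27 = 1.5 h.
- A never-blocked subject with full movement at 8 and 12 h would enter as more than 8 − 1.5 = 6.5 h, if those looks count as an offset.

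**3. Effect on a Kaplan-Meier median.** Take 20 durations of 4, 8, …, 80 h. With all as events, the median is the 10th value, 40 h. If the shortest k are censored, the curve reaches 0.5 halfway through the remaining 20 − k:

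- k = 2: 9th of 18, 12 + 8×4 = 44 h
- k = 4: 8th of 16, 20 + 7×4 = 48 h
- k = 6: 7th of 14, 28 + 6×4 = 52 h

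**4. Simulated medians.** Assumptions: 20 per arm, lognormal durations (log-SD 0.5), incision at 1.5 h, the scheduled looks, first post-surgery look at 3 or 8 h, and 1,500 data sets per setting. Under Reading A, the rise in the arm median against the same durations counted as events was:

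| Affected of 20 | True median 18 h | 30 h | 45 h |
|---|---|---|---|
| 1 | 0.0–0.1 h | 0.7–0.9 h | 0.6 h |
| 2 | 0.2 h | 1.6–1.9 h | 1.4–1.8 h |
| 4 | 0.5 h | 3.4–3.9 h | 3.7–3.9 h |

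Repeat runs at 30 h with 4 affected gave 3.1 to 3.8 h, and 3.9 to 4.4 h against the midpoint-onset fix below. Under Reading B the median equals that from silently dropping never-blocked subjects (difference 0.0 h). At 30 h it exceeds the median with them scored as zero duration by 1.8–1.9, 3.7–3.8 and 7.6–7.8 h for 1, 2 and 4 affected.

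**5. Log-rank test, Reading A.** Identical true durations (median 30 h), four strata standing in for the SAP's age and height groups, 4,000 trials per setting, Monte Carlo error about 0.3–0.5 points:

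| Affected, arm 1 / arm 2 | Rejection, plan | Rejection, fix |
|---|---|---|
| 10% / 10% | 3.8–3.9% | 4.1–4.6% |
| 20% / 20% | 3.8–4.0% | 5.2–5.3% |
| 10% / 5% | 4.4–4.7% | 4.9–5.0% |
| 20% / 5% | 5.8–6.0% | 5.2–5.7% |
| 30% / 5% | 8.9–9.4% | 5.4–5.6% |

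A cruder unstratified simulation (Weibull durations) with 20%, 30% or 40% affected in one arm only gave 10.4%, 17.8% and 28.1%, against 5.4–5.6% with events counted.

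**6. Power.** Schoenfeld power is Φ(√(d/4)·|ln HR| − 1.96) for d events in total. At an assumed hazard ratio of 0.5 it is 0.592 for 40 events, 0.548 for 36, 0.500 for 32 and 0.450 for 28. These correspond to 0, 2, 4 and 6 events lost per arm.

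**The case against.** The strongest reply is that Reading A strains the motor wording. Onset is the earliest blocked look, with no pre-surgery limit, and onset is censored only in a subject who never loses motor function. A subject first seen blocked at 8 h has lost it. Under Reading B the median matches simple exclusion, and the larger shifts arise only from scoring block failures as zero, which is a different estimand. The example's 6.5 h is also a worst case: Protocol 13.6 provides recovery-room assessments, and unscheduled looks around surgery are allowed. Small numbers matter little. At 30 h with 1 of 20 affected the median did not move in about 75% of data sets, and with 2 of 20 in about 60%. The sampling SD of an arm median is about 8.4 h, and the visit grid alone adds about 9 h. Protocol 11.4 reports similar onset in the pilot.

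Much of this stands as to size. It does not rescue the rule. Sections 6.3.1 and 6.3.2 tie onset looks to before surgery and offset looks to after it, and a duration from surgery start to offset makes sense only if an offset can exist without a pre-surgery onset. Reading A is therefore a live reading, and the two readings code the same subject differently. That the curve can only rise follows by construction from turning events into censorings; the simulations supply only the size. The 6.3.1 sentence on both onset and offset reads "If both onset and offset assessment time, interval censored" in the available text. Words have evidently been lost in extraction, and nothing here rests on it.

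**Conclusion.** The concern holds. The rationale in SAP 9.5.2.4 is sound where offset was not reached and unsound where offset was recorded without an achieved onset. In that case the duration cannot exceed offset minus last negative look, and it may be shorter than the value entered. Which subjects fall under the rule is not clearly defined.

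The effect on an arm median is small for one affected subject and about 3 to 4 h for 4 of 20 when the true median is 30 or 45 h. Equal affected shares do not fully protect the ratio of medians. With 4 of 20 affected, an arm with a true median of 18 h shifts by 0.5 h and one at 30 h by 3.4–3.9 h, so the ratio can move when true durations differ. Test size is essentially unchanged without a large imbalance, and no such imbalance is shown. Affected counts, true medians and the hazard ratio are all assumptions. The fourth secondary endpoint and the sensory-duration summaries are affected; the primary endpoint is not. The rule should be fixed, since it is wrong as written and cheap to correct.

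**What to change.** 1. State that a block first recorded after surgery has achieved onset, placed between the last negative and first positive look (as an interval or its midpoint), using recovery-room and unscheduled assessments as well as scheduled ones.
2. For any subject with a block recorded at any assessment, count a recorded offset as an event. Right-censor only when offset was not reached.
3. Keep subjects with no recorded block out of rule 2. Report them as block failures by arm, and pre-specify how they enter the duration analysis, but not as positive censored times.
4. Delete the rationale sentence in 9.5.2.4, reconcile it with the left-censored label in 6.3.1, apply the same rule to sensory block, and report the number of affected subjects per arm.

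The cost is SAP wording and programming. No new data are needed.

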9.5.3. Subgroup Analysis for the Primary and First Secondary Efficacy Endpoints

The analysis of the primary and the first secondary endpoints will be repeated for select subgroups such as

- Age (<45, and \geq 45),
- Sex
- Race (White and Non-White),
- BMI (<25, 25 to <30, and \ge 30+ kg/m²)
- Height (<165 cm, and \geq 165 cm)
- Site
- Surgical Type

9.5.4. Exploratory Endpoints

Assessment of subject satisfaction with pain control using International Pain Outcome (IPO) at 96 hours will be summarized by treatment group.

Current pain intensity collected 0 to 96 hours post surgery will be summarized by treatment group and analyzed for between treatment difference using ANCOVA at each scheduled time point. See Section 9.5.1 for model specification. This analysis will use wWOCF-imputed pain intensity data set (see Section 9.2.2A).

"Average" and "worst" pain score over the last 24 hours will be summarized by treatment group daily from POD1 through POD14. They will also be analyzed each day using ANCOVA (see Section 9.5.1).

AUC of "average" and "worst" pain scores will be calculated for each subject from POD1 through POD4 and through POD14 using the ranctangular area method as follows.

$$AUC_{0-4} = \sum_{i=\text{POD1}}^{POD4} p_i \text{ and } AUC_{0-14} = \sum_{i=\text{POD1}}^{POD14} p_i$$

The ranctangular method is chosen because the pain score here is already a summary of the last 24 hours pain by the patient.

For patients with monotone missing, (ie, once missing, all the following days are missing), the last observation carried forward (LOCF) will be applied to impute the missing daily scores. For patients with intermittent missing, the missing daily scores are imputed as follows.

$$p_x = \left(p_y + p_z\right) \frac{x - y}{z - y},$$

where x is the day with missing pain score, y and z are the days with non-missing pain scores closest to but before and after Day x, respectively. As an example, suppose Day 2 and Day 3 are missing, but Day 1 and Day 4 are collected, Day 2 and Day 3 pain scores are imputed as follows.

$$p_2 = (p_1 + p_4) \frac{2-1}{4-1} = 1/3(p_1 + p_4), \ p_3 = (p_1 + p_4) \frac{3-1}{4-1} = 2/3(p_1 + p_4).$$

For subjects with missing score for the first a few days, the first observation will be carried backward for the missing daily scores. AUC of "average" and "worst" pain scores will be summarized by treatment group. The between group difference will be analyzed using ANCOVA similar to the sensitivity analysis for the primary efficacy endpoint (Section 9.5.1).

A listing of admission and discharge to the surgical facilitate and PACU, postsurgical and pain medications will be provided.

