13.1.1. Pain Intensity Assessment

Pain intensity will be assessed using an 11-point NRS (0-10) as follows:

- Pain intensity scores (using the NRS) measured as “How much pain are you experiencing right now?” will be assessed:
 - Upon arrival in the PACU (± 5 min)
 - Every 15 mins in the PACU (± 5 min)
 - Prior to PACU discharge (± 5 min)
 - Every 6 hours from the end of surgery until 96 hours: 6 h (± 2 h), 12 h (± 2 h), 18 h (± 2 h), 24 h (± 2 h), 30 h (± 2 h), 36 h (± 2 h), 42 h (± 2 h), 48 h (± 2 h), 54 h (± 2 h), 60 h (± 2 h), 66 h (± 2 h), 72 h (± 2 h), 78 h (± 3 h), 84 h (± 3 h), 90 h (± 3 h), and 96 h (± 3 h)

- If a subject is asleep, the subject will not be awakened to assess pain. If the subject awakens within the assessment window, a pain score will be collected then
- Subjects will be instructed not to complete the NRS pain intensity score after any physical activity, including the motor block assessment. If that is not possible, to assess pain intensity at rest, the subject should rest quietly in a supine or seated position that does not exacerbate his or her postsurgical pain for 5-10 minutes before entering the pain score using the NRS. Subjects will also be required to provide unscheduled pain assessments prior to consumption of any breakthrough pain medication.
- An unscheduled NRS assessment will be obtained immediately prior to administration of any breakthrough pain medication until 96 hours post-surgery.
- Pain intensity scores (NRS) once daily at 21:00 (± 3 h) from POD 1 to POD 14 measured as “What was your **worst** pain in the last 24 hours?”
- Pain intensity scores (NRS) once daily at 21:00 (± 3 h) from POD 1 to POD 14 measured as “What was your **average** pain in the last 24 hours?”

Subjects will be instructed to focus all NRS pain intensity ratings on the operative ankle/foot, and not other locations where they may be experiencing pain.

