9.2.2. NRS Pain Intensity Scores

Pain scores obtained during the opioid medication window will be replaced with the worst observation carried forward (wWOCF). For this study, the prescribed opioid pain medication

is oxycodone. However, morphine, hydromorphone, or other opioids may be used. The durations of the analgesic effect for various opioids are listed in Table 6.

· · · · · · · · · · · · · · · · · · ·	Route	Window Used to		
Medication		Replace NRS		
Oxycodone, Oxycocet, Percocet, acetaminophen-	PO, IM, IV, SC	6 hours		
oxycodone, Oxycontin				
Morphine	IV, PO, SC	4 hours		
Hydromorphone (Dilaudid), Hydromorphone	IV	2 hours		
hydrochloride				
Hydromorphone (Dilaudid), Hydromorphone	PO, IM, SC	4 hours		
hydrochloride				
Hydrocodone	РО	6 hours		
Fentanyl	IV, PO, IM	6 hours		
Hydrocodone combination product - Vicodin, Norco,	PO	6 hours		
Lorcet, Lortab, hydrocodone-acetaminophen				
Codeine combination product - Tylenol 3,	РО	6 hours		
acetaminophen-coedine, Paracetamol Forte, Tylenol 4				
Ultram, Tramadol, Tramacol hydrochloride	РО	6 hours		
PO = oral, IV = intravenous, IM = Intramuscular, SC = subcutaneous.				

Table 6: Opioid Pain Medication Window

If other opioid pain medications not listed above are given, the window will be determined prior to the database lock and unblinding. If a combination opioid product is given, the window will be determined by the opioid part of the medication.

For the primary efficacy endpoint of AUC of NRS pain score 0-96 post-surgery, after applying the visit windows (Section 5 Table 3) and wWOCF to all scheduled/unscheduled pain scores, remaining missing data at each scheduled time point (6 h, 12 h , 18 h, 24 h, 30 h, 36 h, 42 h, 48 h, 54 h, 60 h, 66 h, 72 h , 78 h, 84 h, 90 h, and 96 h) will be imputed using the Rubin's (1987) multiple imputation procedure. This procedure replaces each missing value with a set of plausible values that represent the uncertainty about the right value to impute. The procedures of wWOCF and multiple imputation are described in the order as follows.

A. For subjects who take an opioid pain medication, their NRS scores recorded within the window of controlled type of opioid medication (see Table 6) will be replaced by the 'worst' observation. The worst observation will be the highest NRS score from the end of previous opioid window (excluding the exact end of the window) or the end of surgery whichever is later. The NRS score at the time of opioid pain medication

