administration will be included in this calculation. Note (1) the NRS score in the window that is higher than the worst value to be carried forward, this "higher" value will not be overwritten. Instead, the worst value will be replaced by this "higher" value and continue carrying forward until the end of the window. (2) if the scheduled NRS score within the window is missing, it will be imputed with this worst value.

B. After the wWOCF imputation described above, if there are still missing NRS scores at scheduled time points, they will be imputed using the multiple imputation procedures using the Markov Chain Monte Carlo (MCMC) method (Schafer 1997). This imputation will be carried out within each treatment group using SAS PROC MI. Thirty imputations will be conducted. To minimize the effect of data skewness on the imputation result, the NRS score is log-transformed [y=log(x+0.5), where y is the transformed score, x is the raw NRS score, and constant 0.5 is added to avoid log(0)] prior to the imputation and back-transformed after the imputation. In order to achieve the stationary distribution and to avoid dependency within samples generated by MCMC method, the number of iterations for the burn-in period will be set to 2000 and the number of iterations between two consecutive samples will be set to 1000.

For the imputed NRS scores, the associated time will be assigned with the exact scheduled time, eg, 48.0 h.

To better simulate the observed NRS pain score, all imputed scores will be rounded to become a number between 0.0 and 10.0 with 1 decimal place.

- C. The AUC at various time intervals will be derived as described in Section 9.5.1 from the imputed NRS scores. For each subject, there will be 50 sets of AUC from the 50 imputed data sets.
- D. The endpoints derived in Step C will be analyzed as described in Section 9.5.1 for each imputed data set.
- E. Rubin's (1987) synthesizing procedure will be applied to synthesize analysis results from the 50 imputed data sets. SAS PROC MIANALYZE will be used for this analysis. The least squares mean (LSM) and standard error (SE) for each treatment group, and the LSM, SE, 95% CI and p-value for the between treatment difference in AUC will be computed from this analysis.

The SAS pseudo-code for multiple imputations and analysis is as follows.

** Step (b) uses MCMC method to create fully imputed data sets

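### The exploratory by-time-point pain analysis fills missing scores only inside an opioid window, so who is analysed at sleep-affected time points depends on opioid use after randomisation

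*SAP*

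**What the plan says.** Current pain intensity through 96 hours is an exploratory endpoint (SAP 8.1.3). SAP 9.5.4 summarises it by arm and has it "analyzed for between treatment difference using ANCOVA at each scheduled time point". On the data source it says: "This analysis will use wWOCF-imputed pain intensity data set", with a reference to Step A of SAP 9.2.2.

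Step A concerns only opioid takers inside a drug-specific window (SAP Table 6, 2 to 6 hours; 6 hours for oxycodone): "For subjects who take an opioid pain medication, their NRS scores recorded within the window of controlled type of opioid medication" are replaced by the worst score. On that score: "The worst observation will be the highest NRS score from the end of previous opioid window" or from the end of surgery, whichever is later. Note (2) extends this to gaps: "if the scheduled NRS score within the window is missing, it will be imputed with this worst value". Step A has no rule for a missing score outside a window.

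That gap is closed only in Step B, which says: "After the wWOCF imputation described above, if there are still missing NRS scores at scheduled time points, they will be imputed using the multiple imputation". SAP 9.2.2 introduces the imputation for the primary AUC, and 9.5.4 does not cite Step B.

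Protocol 13.1.1 makes missing night scores part of the design: "If a subject is asleep, the subject will not be awakened to assess pain". A score is taken if the subject wakes within the collection window. SAP Table 3 lets any scheduled or unscheduled score within the time bin fill the slot.

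**The concern.** Take two subjects asleep at the same scheduled time, neither with a score in the bin. The one inside an opioid window enters the ANCOVA at the worst score. The one outside a window does not enter at all, whether opioid-free or a user whose window has closed. The SAP does not say that such a subject is dropped; it follows because no other rule applies.

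Inclusion at that time point therefore depends on opioid use after randomisation. Treatment is expected to change opioid use: total consumption is the first secondary endpoint. Two things are at stake in the exploratory results: the level of each arm's pain curve at sleep-affected times, and the treatment difference and test at those times. SAP 9.5.4 names no sensitivity analysis for this.

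**Working it through.** The plan gives no figure on this point to reproduce. The documents also give no sleep rates, opioid-use rates or by-time means, so every input below is an assumption shown over a range.

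**Inputs for one time point in one arm.** u is the share inside an opioid window, always scored, with mean W. F is the mean of the others, and s is the share of those others with no score in the bin.

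**Formulas.**
- Full-data mean = uW + (1−u)F.
- Step A mean = [uW + (1−u)(1−s)F] / [u + (1−u)(1−s)].
- Subtracting, the upward shift = s·u(1−u)(W−F) / [1 − s(1−u)]. It is positive whenever s > 0, W > F and u lies strictly between 0 and 1.

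**Example: W = 6, F = 2, s = 0.5, u = 0.1 (EXPAREL) and 0.4 (bupivacaine).**
- EXPAREL: full 0.6 + 1.8 = 2.40; Step A (0.6 + 0.9)/0.55 = 2.73.
- Bupivacaine: full 2.4 + 1.2 = 3.60; Step A (2.4 + 0.6)/0.70 = 4.29.
- Difference: −1.20 in full data, −1.56 under Step A.
- Subjects analysed out of 40 per arm: 22 and 28.

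**Other cases (W = 6, F = 2; difference is EXPAREL minus bupivacaine).**

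| u, EXPAREL / bupivacaine | s | Full-data difference | Step A means | Step A difference | Shift | Analysed of 40 |
|---|---|---|---|---|---|---|
| 0.1 / 0.4 | 0.1 | −1.20 | 2.44, 3.70 | −1.26 | −0.06 | 36, 38 |
| 0.1 / 0.4 | 0.3 | −1.20 | 2.55, 3.95 | −1.40 | −0.20 | 29, 33 |
| 0.1 / 0.4 | 0.5 | −1.20 | 2.73, 4.29 | −1.56 | −0.36 | 22, 28 |
| 0.3 / 0.6 | 0.5 | −1.20 | 3.85, 5.00 | −1.15 | +0.05 | 26, 32 |
| 0.5 / 0.8 | 0.1 | −1.20 | 4.11, 5.27 | −1.16 | +0.04 | 38, 39 |
| 0.5 / 0.8 | 0.5 | −1.20 | 4.67, 5.56 | −0.89 | +0.31 | 30, 36 |
| 0.5 / 0.9 | 0.1 | −1.60 | 4.11, 5.64 | −1.53 | +0.07 | 38, 40 |

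**Wider grid.** With u for EXPAREL 0.1 to 0.5, u for bupivacaine 0.1 to 0.4 higher, s 0.1 to 0.6, W 5 to 7 and F 1 to 3, the EXPAREL mean rises by 0.02 to 1.35 points. The bias in the difference runs from −0.65 to +0.94 and favours EXPAREL in 54% of the grid, so its direction is not fixed.

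**Tests.** In 3000 simulated two-sample t-tests per case (40 per arm, SD 2, s = 0.5), full-data and Step A rejection rates were:
- 57% and 53% at u 0.1/0.4
- 49% and 36% at 0.3/0.6
- 49% and 29% at 0.5/0.8
- 5.3% and 5.5% at equal u of 0.4 and equal sleep, where the difference is unbiased

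With u = 0.4 in both arms but s of 0.5 in one and 0.2 in the other, the closed form gives a spurious difference of 0.47.

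**What imputation would recover.** A simulation used 8000 subjects per arm, mean pain 2.5 and 4.0, subject SD 1.8, residual SD 1.3 and opioid use of 19% and 36%, rising with pain. Half of the opioid-free subjects were missing at 12, 36, 60 and 84 h. True means at those points were 2.68 and 4.17 (difference 1.49). Step A gave 3.11 and 4.73 (difference 1.62). Imputation within arm on log(x+0.5) gave a difference of 1.52 and about halved the error in the arm means.

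**The case against.** The case for leaving the plan alone is substantial.

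- **No decision rests on it.** The endpoint is exploratory and outside the five-step hierarchy of SAP 9.5. The primary AUC uses Step B. This stands, and it sets the weight of the point.
- **Missingness may be low.** Staff may collect within ±2 h (±3 h from 78 h), including on waking, and Table 3 accepts any score in adjoining bins. Suppose surgery ends evenly between 09:00 and 17:00 and sleep is unbroken from 23:00 to 07:00. The 12, 36 and 60 h windows lie wholly within sleep only for surgery ending 13:00 to 17:00 (4/8 = 50%), and the 84 h window only for 14:00 to 16:00 (2/8 = 25%). With sleep from 23:00 to 05:00 these fall to 25% and about 0%. So 50% is near a ceiling.
- **Coverage does not simply track opioid use.** A score is required before any breakthrough medication, including acetaminophen and NSAIDs (Protocol 11.7). Cohort 1 also has blood draws at 12, 60 and 84 h after the block, which make unbroken sleep less likely. Both reduce s by an unknown amount.
- **The error is small against the noise.** In the last simulation it is 1.62 − 1.49 = 0.13. With a total SD of √(1.8² + 1.3²) ≈ 2.2 and 40 per arm, the SE is about 2.2 × √(2/40) ≈ 0.5, so the bias is about a quarter of one SE. This holds for that scenario; other inputs give more.
- **Imputation is imperfect.** If subjects sleep because pain is low, missing at random is doubtful too. This stands as a limit on the fix.

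A reader might infer that every sleeping opioid user is given the worst score. The text supports this only inside the drug window, and subjects who are awake in a window get the worst score too, as the plan's intended opioid adjustment. A reader might also infer that the by-time curves must agree with the primary AUC. No section says they illustrate it, and the AUC also uses PACU and unscheduled scores at exact times, so means at 16 nominal points would not reproduce it even after the change.

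**Conclusion.** The point holds as a minor one. As written, SAP 9.5.4 handles missing scores unequally inside and outside an opioid window, so inclusion in each by-time ANCOVA depends on opioid use after randomisation.

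Arm means at sleep-affected times are biased upward if the omitted sleepers have lower pain. The treatment difference is biased only if opioid use or sleep differs between arms, and then in either direction. The documents do not support a claim that the bias favours EXPAREL, that false positives rise when the arms are alike, or that the primary result is at risk.

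The size is unknown. With assumed means of 6 and 2, the shift in the difference is about 0.07 NRS points or less when 10% of those outside a window lack a score. At 50%, the difference is for example 1.56 against 1.20 with 10% and 40% in a window. One part of SAP 9.5.1 was not in the text reviewed. 9.5.4 refers to 9.5.1 for the model but names its own data set, so the conclusion does not appear to depend on the missing part.

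**What to change.** In SAP 9.5.4, replace the data-set sentence with wording such as: the by-time-point means and ANCOVA will use the data sets from Section 9.2.2 Step B (wWOCF followed by multiple imputation), with the ANCOVA fitted to each data set and pooled by Rubin's rules. For each arm and time point, report the numbers observed, filled by wWOCF and imputed. Keep the Step-A-only results as supportive.

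The cost is one sentence and one pooled analysis per time point. The sample code in SAP 9.2.2 already outputs completed scores from 6 to 96 h and shows the pooling step, so no new data are needed. The number of imputations should be settled in the same edit: the Step B text says thirty, while the code and Steps C and E say 50. The downside is that imputation assumes missing at random and corrects only partly for pain during sleep.
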